4.2.2 Secondary Efficacy Endpoint

The secondary endpoints for this study are the change from baseline* to each applicable time point (see Table 2) for the following parameters:

- Change from baseline* to each applicable time point (see Table 2) for the following parameters:
 - TEWL measurements
 - Clinical Grading of Wound Healing – Erythema
 - Clinical Grading of Wound Healing – Edema
 - Subject self-assessment questions 1, 3, and 5.
 - Composite Scar Score – calculated as the sum of the individual parameters on the Manchester Scar Scale (Color, Finish, Contour, Distortion and Texture). Composite Scar Scores range from 5 to 18, with 5 representing clinically best scars and 18 representing clinically worst scars.
- Subject self-assessment questions 2 and 4 at each applicable time point.

*Baseline is considered the Day 0 Pre-Wound time point for all endpoints except the subject self-assessment questions. For the subject self-assessment questions, baseline is considered the Day 0 Post-Wound time point.

[REDACTED]

[REDACTED]

[REDACTED]

[REDACTED]

[REDACTED]

[REDACTED]

[REDACTED]

4.3 Safety Assessments and Endpoints

Safety assessments consist of Adverse Events.

- Number and percentage of subjects with treatment-emergent adverse event
- Number and percentage of subjects with treatment-related adverse event
- Number and percentage of subjects with serious adverse event

4.4 Other Endpoints

Not applicable.

4.5 Covariates

For the analyses of Change from Baseline in TEWL measurements, erythema, edema, the composite scar score, corresponding baseline value will be included in the models as covariate.

5 HANDLING OF MISSING VALUES

No imputation of missing data will be performed.

6 STATISTICAL METHODOLOGY AND STATISTICAL ANALYSES

The Biostatistics Group at the Sponsor will be responsible for the statistical analysis of the primary and secondary endpoints. Summary statistics will be provided at each time point for the primary and secondary efficacy and safety assessments. For continuous variables, descriptive summaries will include number of subjects, mean, standard deviation, median, minimum and maximum values. Distributions of categorical variables

Protocol CCSTOH001689
Statistical Analysis Plan

will be summarized by presenting the number and percent of subjects in each response category.

6.1 Statistical Hypotheses

The between-product comparison will be based on the median complete healing times. The following null hypothesis will be tested using the bootstrap re-sampling method

$$H_0: M_1 = M_2$$

against the two-sided alternative

$$H_A: M_1 \neq M_2$$

where M_1 and M_2 are the median complete healing times of the two product groups to be compared, respectively.

6.2 Statistical Decision Rules

This is a proof-of-principle study, all hypothesis tests will be conducted at 0.05 level without adjustment of multiple comparisons, it serves as exploratory purpose.

6.3 Statistical Methods

Summary statistics will be provided at each time point for the primary and secondary efficacy.

Time to complete healing will be analyzed using a survival analysis method. The survival function (cumulative percentage of wounds healed at each time point) will be estimated by the Kaplan-Meier method for each treatment separately. The median time to complete healing will be derived from the estimated survival functions and be compared using the bootstrap re-sampling method.

The pairwise comparison of median complete healing times is performed by the following steps:

- 1) Independently take $B=200$ bootstrap samples with subject as the sampling unit. Each bootstrap sample has the same size as the original sample size and is obtained by sampling subjects with replacement with the original time to complete healing data, say $\{(t_1^b, \dots, t_8^b), b = 1, \dots, B\}$.
- 2) Within each bootstrap sample, estimate the median survival time using KM method for each treatment separately, say $\{\hat{m}_i^b : i = 1, 2, \dots, 8, b = 1, \dots, B\}$.
- 3) Calculate the pairwise difference in median times to complete healing $\hat{\tau}^b = \hat{m}_{i1}^b - \hat{m}_{i2}^b, b = 1, \dots, B$.

Protocol CCSTOH001689
Statistical Analysis Plan

4) Estimate the variance of the median time difference by

$$v(\hat{\tau}) = \frac{1}{B-1} \sum_{b=1}^B (\hat{\tau}^b - \bar{\hat{\tau}})^2$$

$$\text{where } \bar{\hat{\tau}} = \sum_{b=1}^B \hat{\tau}^b / B$$

The null hypothesis of $H_0: M_{i1} = M_{i2}$ can be tested by the following test statistics

$$z = \frac{\hat{M}_{i1} - \hat{M}_{i2}}{\sqrt{v(\hat{\tau})}}$$

Under the null hypothesis, this test statistics asymptotically follows the standard normal distribution. Hence the 2-sided p-value and the 95% confidence interval can be calculated by

$$p = 2 \times \{1 - \Phi(|z|)\}$$

and

$$(\hat{M}_{i1} - \hat{M}_{i2} - z_{0.975} * \sqrt{v(\hat{\tau})}, \hat{M}_{i1} - \hat{M}_{i2} + z_{0.975} * \sqrt{v(\hat{\tau})})$$

where $\Phi(s)$ is the cumulative probability function of the standard normal.

TEWL measurements, erythema, edema, the composite scar score, and self-assessment questions 1, 3, and 5 will be analyzed within-treatment and between-treatment. The within-treatment comparison will be performed at each post-baseline time point by comparing the post-baseline scores with the baseline score within each treatment using the paired t-test. The between-treatment comparison will be performed by comparing the change from baseline between treatments using a mixed effect analysis of covariance (ANCOVA) model. The ANCOVA model will include the treatment as the factor and the baseline value as the covariate. The model will include subject as a random effect to incorporate the within-subject correlation. The adjusted mean of each product from the ANCOVA model will be compared between the IPs and the negative control, between the IPs and the IP - █ between the IPs (except the IP - █ and the IP – Benchmark Control 1, and between the IPs (except the IP - █ and the IP – Benchmark Control 1) and the IP – Benchmark Control 2).

The mixed effect analysis of covariance model can be performed by the following SAS codes

PROC MIXED DATA = <dataset>;

CLASS subjid treatment;

```
MODEL chg = treatment baseline/solution ddfm = contain;  
RANDOM subjid ;  
LSMEANS treatment/diff cl;  
ESTIMATE "IP - █ vs. Negative Control" treatment 1 0 0 0 0 0 0 -1 /cl;  
ESTIMATE "Product #1 vs. Negative Control" treatment 0 0 0 1 0 0 0 -1 /cl;  
...  
RUN;
```

Note:

Self-assessment questions 2 and 4 will be summarized by frequency distribution for each treatment at each collection time point.

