DOSE AND MODE OF APPLICATION	The auxiliary product will be provided to to on their forearms and for all body cleans body cleanser for the duration of the study. The IPs will be applied to 7 of the 8 wou Baseline (Day 0) by trained staff act randomization scheme. The last wound so an untreated control. IPs* will be removed at the beginning of (Visit 3) through Day 16 (Visit 18) and report study visit from Day 1 (Visit 3) through Day 16 (Visit 3)	ing in place of their regular dy. Ind sites for each subject at cording to a preassigned ite will be left uncovered as each study visit from Day 1 placed** at the end of each by 15 (Visit 17).	
STUDY DURATION	The study will be conducted over approximately 5 weeks with visits at Screening (Day -7 to Day -3), daily from Baseline (Day 0) to Day 16, on Day 21, and at the end of the study on Day 28.		
METHODOLOGY	 Clinical Grading of Wound Healing Parameters (erythema, edema, epithelial confluence, crusting/scabbing, smoothness, and general wound appearance) Scarring Assessment TEWL Measurements Self-Assessment Questionnaire 		
MEASUREMENT AND/OR EVALUATION SCHEDULE AND ASSOCIATED SUCCESS	The following evaluations will be conducted the indicated time points: • Clinical Grading of Wound Healing P		

Different Adhesive Bandages Protocol Number: CCSTOH001689

Version & Date: Amendment 3: Final Version 4.0, 28 Aug 2019

	 and general wound appearance) – Day 0 through Day 16* Scarring Assessment - Day 0 and Day 28 TEWL Measurements - Day 0 through Day 14* Self-Assessment Questionnaire - Day 0 through Day 4
	Success Criterion: •
	All statistical analyses will be performed using the Statistical Analysis System (SAS) v9.4 software. The statistical analysis will be performed by the Biostatistics Group at the Sponsor. All collected assessment data will be listed individually for all subjects. The following descriptive statistics will be presented: mean, standard
STATISTICAL METHODS	deviation (SD), median, minimum, and maximum. Percentage change from baseline will also be presented. The primary endpoint, time to complete healing, is defined as the time (in days) elapsed from the time of wound creation to 12PM of the day on which the wound is evaluated as "completely healed."

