8.1. SAMPLE SIZE DETERMINATION

As this is a proof-of-principle study to estimate the effect size, and no prior data are available on these endpoints from previously conducted studies of similar study design on these prototypes, a sample size of 40 with a target completion of at least 30 subjects should provide a reliable estimation of the effect size.

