8.3. ENDPOINTS

8.3.1. Primary Endpoints

The primary endpoint of the study will be "Time to Complete Healing" defined as the time (in days) elapsed from the time of wound creation to 12 PM of the day on which the composite healing score (calculated from the clinical grading of wound healing parameters, as defined below) first meets the complete healing criterion of being at least a score of 8. If a composite healing score does not meet the complete healing criterion by Day 16, the time to complete healing will be censored at the last day on which the composite healing score is available.

The composite healing score will be calculated from the clinical grading of wound healing parameters as follows:

Composite Healing Score = [general wound appearance score + smoothness score + epithelial confluence score] – [erythema score + edema score + crusting/scabbing score]

The composite healing score on a 25-point scale (-12 thru +12) is indicative of the extent of wound healing and will be calculated for each wound site at each evaluation day.

Time to complete healing will be analyzed using a survival analysis method. The survival function (cumulative percentage of wounds healed at each time point) will be estimated by the Kaplan-Meier method for each treatment separately. The median time to complete healing will be derived from the estimated survival functions and be compared using the bootstrap re-sampling method.

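### The primary median comparisons rest on a bootstrap standard error from only 200 resamples with no visible seed; a larger B and a stated seed would be a free, low-priority improvement

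*SAP*

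**What the plan says.** SAP 6.3 sets out the comparison of median healing times in steps. Step 1 fixes the number of resamples: "Independently take $B=200$ bootstrap samples with subject as the sampling unit". Step 2 takes a Kaplan-Meier median per treatment within each resample. Step 3 is to "Calculate the pairwise difference in median times to complete healing". Step 4 takes the sample variance of the 200 differences. The square root of that variance divides the observed difference to give z, and it also scales the interval: "Hence the 2-sided p-value and the 95% confidence interval can be calculated by".

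SAP 6.2 states that "all hypothesis tests will be conducted at 0.05 level without adjustment of multiple comparisons" and labels the tests exploratory.

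Neither document's visible text gives a seed, a resampling procedure or a check on Monte Carlo error. No redaction mark appears inside the bootstrap steps. Later in SAP 6.3 there is code for the secondary endpoints, introduced by "The mixed effect analysis of covariance model can be performed by the following SAS codes"; none is visible for the bootstrap. Protocol 8.3.1 says only that the medians are "derived from the estimated survival functions and be compared using the bootstrap re-sampling method", and the protocol synopsis names the software: "All statistical analyses will be performed using the Statistical Analysis System (SAS) v9.4 software".

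**The concern.** A standard error computed from a finite number of resamples has noise of its own, apart from sampling variation in the trial. That noise enters every primary p-value and every primary interval. With B = 200 it is large enough to move a result near 0.05 from one side of the threshold to the other, and the SAP does not fix which set of resamples will be used.

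Two things are at stake. One is reproducibility: a second programmer following the SAP as written could reach a different reading of a borderline comparison. The other is the stated precision of the healing-time differences. Protocol 8.1 justifies the sample size by saying that it "should provide a reliable estimation of the effect size", and the interval is how that reliability will be shown.

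**Working it through.** **Inputs from the documents.** B = 200; only the standard deviation of the resampled differences is used; standard normal reference; two-sided 0.05, unadjusted (SAP 6.1 to 6.3); eight treatments; 40 subjects with at least 30 completing (protocol 8.1). The documents state no Monte Carlo precision, power, SD or effect size, so there is no figure of the plan's own to reproduce. The critical value of 1.960 agrees with the two-sided 0.05 level and the 95% interval.

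**Monte Carlo error of the standard error.** If the resampled differences are roughly normal, the relative SD of the standard error is 1/√(2(B−1)). At B = 200 this is 1/√398 = 0.050. The 95% range of the ratio of the reported standard error to its unlimited-resample value is √(χ²/(B−1)), at the 2.5% and 97.5% quantiles of chi-square on B−1 degrees of freedom. At B = 200 this is 0.902 to 1.098. The interval half-width moves in the same proportion, about ±10%.

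**Effect on a borderline p-value.** Take a comparison with z = 1.96 at unlimited resamples. At B = 200 the reported z runs from 1.96/1.098 = 1.785 to 1.96/0.902 = 2.173. With p = 2(1−Φ(z)), p runs from 0.074 down to 0.030.

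| B | relative SD of SE | 95% range of SE ratio | reported p when the unlimited-resample p is 0.05 |
|---|---|---|---|
| 200 | 5.0% | 0.902–1.098 | 0.030–0.074 |
| 1,000 | 2.2% | 0.956–1.044 | 0.040–0.060 |
| 2,000 | 1.6% | 0.969–1.031 | 0.043–0.057 |
| 10,000 | 0.7% | 0.986–1.014 | 0.047–0.053 |

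**Where the reading depends on the seed.** Let q be the chance that one seed gives p < 0.05. Two seeds then disagree with probability 2q(1−q). At B = 200, by unlimited-resample p:

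| unlimited-resample p | two seeds disagree |
|---|---|
| 0.027 | 1% |
| 0.032 | 6% |
| 0.04 | 27% |
| 0.05 | 50% |
| 0.06 | 34% |
| 0.077 | 5% |
| 0.087 | 1% |

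The material zone is therefore about 0.03 to 0.08. At B = 10,000 it narrows to about 0.047 to 0.053. At exactly 0.05 two seeds still disagree half the time at any B; a larger B only narrows the zone.

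**Check on Kaplan-Meier medians.** The normal approximation was tested on simulated paired healing times with daily grading and censoring at Day 16. The inputs were assumed: n = 30 or 40, mean about 10 days, between- and within-subject SD 1.5 days each, shift 1.2 days. The median relative SD of the standard error at B = 200 was about 5% (3.6% to 8.6% across datasets). One simulated dataset with n = 40, a 1.00-day difference and p = 0.048 at near-unlimited resamples gave p from 0.026 to 0.079 at B = 200, and was significant in 54% of runs.

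**Number of comparisons.** Eight treatments give 8×7/2 = 28 pairs. If the contrasts listed for the secondary ANCOVA in SAP 6.3 also apply to the medians, there are 7 + 6 + 5 + 4 = 22; the six pairs among the four prototypes drop out. That they apply is an inference, since the SAP lists no pairs for the medians.

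**Share of the noise that B controls.** In simulated trials (n = 30 or 40, SD 1.5 or 2.5 days, three patterns of treatment differences, all assumed), the standard error at B = 200 varied between trials with a coefficient of variation of 18% to 22%. The Monte Carlo part was 5% to 6%, or 6% to 8% of the variance. The rest comes from the number of subjects.

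**The case against.** The strongest reply is that nothing here is an error. The method is pre-specified, resampling whole subjects respects the within-subject correlation, and the tests are exploratory. In simulation under assumed healing times, rejection rates at B = 200 and B = 10,000 differed by at most 0.4 percentage points. All of this stands, and it is why the point is an improvement and not a defect.

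Four stronger readings are tempting, and the documents do not support them.

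- A reader might infer that rerunning the sponsor's program would change the answer. That follows only if the program sets no seed. The program is not available, and a seed in code or in redacted text cannot be excluded. What can be said is that the result depends on the seed chosen and the visible SAP does not fix one.
- A reader might infer that the effect estimates are unreliable. They are differences in Kaplan-Meier medians from the observed data and do not involve B.
- A reader might conclude that product decisions hang on the seed. The success criteria are redacted, so whether any decision uses p < 0.05, or which pairs, cannot be seen.
- A reader might attach a percentage to the chance that at least one of the 28 comparisons changes. Under assumed healing times that chance ran from 19% to 66% at B = 200, depending on the true differences. The documents give no SD, correlation or effect size to narrow it, and 28 is the widest possible family.

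**Conclusion.** The point holds as a free improvement of low priority. At B = 200 the seed alone moves every primary interval width by about ±10% and spreads a p-value of 0.05 over about 0.030 to 0.074. It matters for significance only when the unlimited-resample p-value is about 0.03 to 0.08; clear results do not change. With 22 to 28 comparisons possible, it is plausible that at least one borderline result would differ between seeds, but no firm rate can be given.

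The formula results assume only roughly normal resampled differences, and the simulation with assumed inputs agrees with them. A larger B would not make borderline results dependable in any wider sense, because over 90% of the variance of the standard error in the assumed settings came from having 30 to 40 subjects.

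**What to change.** In step 1 of SAP 6.3, replace 200 resamples with 10,000 (2,000 at the least), and state the random seed there before the analysis is run. Both parts are useful: a seed alone makes a single draw repeatable but leaves its 5% error in place, while a larger B shrinks that error to 0.7% (1.6% at 2,000).

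The hypothesis, the Kaplan-Meier medians, the subject-level resampling and the z-test stay as written. Protocol 8.3.1 gives neither B nor a seed, so the protocol text need not change. The cost is computing time and one edited SAP line. The gain is limited to reproducible borderline p-values and stable interval widths.

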6.6. RANDOMIZATION/IP ALLOCATION AND BLINDING

Upon signing the ICD, each subject will be sequentially issued an eight-digit subject ID. The first four digits will be the center ID, 1001, and the next four digits will be a unique subject identifier assigned in ascending numerical order beginning with 1001 (i.e. subject ID 10011001, 10011002, 10011003, etc.).

Different Adhesive Bandages Protocol Number: CCSTOH001689

Version & Date: Amendment 3: Final Version 4.0, 28 Aug 2019

Qualified subjects will be assigned a randomization number sequentially from the randomization list at the Baseline visit (Visit 2). Once a randomization number has been assigned to a subject, it cannot be reassigned to another subject.

Randomization of the study treatments to the eight wound sites (see section 7.2.3.3; one study treatment per wound site) will be based on a randomization scheme devised by the Biostatistics Group at the Sponsor using assigned treatment codes (A through H).

Due to the nature of the IPs and the study design, it is not feasible to fully blind the IPs or to conceal the treatment assignments from study subjects or from all study personnel (i.e. those involved in applying/removing the IPs, IP accountability, or assessing subject compliance). Staff responsible for IP accountability and IP application/removal (hereafter "unblinded staff") will have access to the randomization schedule in order to accurately administer the study treatments. The unblinded staff will not complete any subject evaluations other than the interview for compliance/AEs.

The PI and staff conducting evaluations other than the interview for compliance/AEs (hereafter "blinded staff") will not have access to the randomization schedule, and the IPs will be kept separate from the blinded staff. Subjects will be instructed not to disclose information about their assigned study treatments to blinded staff, or to discuss any other information that may reveal the treatment assignment.

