7.2.3.2. Randomization

A unique randomization number will be assigned to each subject as described in section 6.6.

Version & Date: Amendment 3: Final Version 4.0, 28 Aug 2019

7.2.3.3. Identification of Test Sites and Application of Temporary (Semi-Permanent) Dot-Tattoos and Test Site Labels

Eight test sites (i.e. wound sites) will be identified on the volar forearms, four on each forearm, as shown in Figure 6.

[figure not shown]

Figure 6. Wound Site Placement

Going from the elbow to the wrist, the test sites on the right volar forearm will be designated test sites 1, 2, 3, and 4, and those on the left volar forearm will be designated test sites 5, 6, 7, and 8. The test sites will be spaced such that the wounds (see section 7.2.4.3.) will be created at least 4.0 cm apart so that the IPs will not overlap when applied.

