7.2.4.3. Wounding Procedure with Er:YAG 2940 Laser (Sciton, Palo Alto, CA, USA)

A certified laser specialist will create 8 uniform wounds on the volar forearms of each subject at the designated wound sites (see section 7.2.3.3) using a Sciton Er:YAG 2940 laser.

- The wounds will be induced with erbium at an energy setting of 12.2 J/cm2
- Number of passes: 3 passes of ~50μm depth per pass
- Each wound will be a circle, 6 mm in diameter
- The wound sites will be at least 4 cm apart, as indicated in section 7.2.3.3.

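### ANCOVA for TEWL, erythema, edema and scar score leaves out test site; adding it is an optional precision gain above a small break-even site effect

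*SAP*

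**What the plan says.** SAP 6.3 and Protocol 8.3.2 describe the between-treatment model in the same terms: "The ANCOVA model will include the treatment as the factor and the baseline value as the covariate". Subject is the random effect. The SAS statement in SAP 6.3 is "MODEL chg = treatment baseline/solution ddfm = contain", and only subject and treatment are class variables. SAP 4.5, which covers TEWL, erythema, edema and the composite scar score, says that the "corresponding baseline value will be included in the models as covariate" and names no other covariate.

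On the design, Protocol 6.6 has "Randomization of the study treatments to the eight wound sites (see section 7.2.3.3; one study treatment per wound site". Protocol 7.2.3.3 fixes the numbering: "Going from the elbow to the wrist, the test sites on the right volar forearm will be designated test sites" 1 to 4, with 5 to 8 on the left arm. Neither document says whether treatments are permuted independently for each subject or balanced over positions.

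On baseline, SAP 4.2.2 says: "Baseline is considered the Day 0 Pre-Wound time point for all endpoints except the subject self-assessment questions". The exception is "For the subject self-assessment questions, baseline is considered the Day 0 Post-Wound time point". SAP 6.2 declares all tests exploratory, at the 0.05 level, without multiplicity adjustment.

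**The concern.** Site is a known design factor. Each subject carries one wound at each of eight positions, and which treatment went where is on record (SAP Appendix 2, listing 16.1.7). If skin near the elbow responds to the laser or heals differently from skin near the wrist, or one arm differs from the other, that difference goes into the residual of the planned model. A pre-wound baseline is measured on intact skin. It can absorb a standing site difference, but not a difference in response or healing.

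What is at stake is the width of the confidence intervals for differences between bandages on these four endpoints. Protocol 8.1 says the study is meant to estimate effect size, so precision matters here even though no power claim is made.

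Self-assessment questions 1, 3 and 5 use the same model but are outside this point. Their baseline is post-wound and can absorb site differences in the response to wounding.

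**Working it through.** The plan gives no figure for a site effect and no power calculation, so there is nothing to reproduce. The check asks when a site term helps.

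**Inputs.** Eight treatments on eight sites, each once per subject (Protocol 6.6, 7.2.3.3). At least 30 completers, up to 40 enrolled (Protocol 5); the ITT set can therefore exceed 30. Two-sided 0.05 is stated for the primary test and taken to apply here. Complete data are assumed. Residual variance is set to 1. The site variance is r (divisor 7), and share = r/(1+r) is the true fraction of within-subject variance left after baseline that is due to site. Shares of 0 to 30% are assumptions.

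**Degrees of freedom.** Without site: 8n − n − 7 − 1 = 202 at n=30 and 272 at n=40. With an eight-level site factor: 195 and 265.

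**Freely permuted sites.**
- Without site, two treatments in one subject sit on two random distinct sites, so the SE of a contrast is √(2(1+r)/n). The planned model estimates this correctly.
- With site, the SE is √(2F/n). F is the variance factor for treatment and site not being orthogonal, about 202/195 = 1.036 at n=30 and 272/265 = 1.026 at n=40. Simulated allocations gave the same means.
- Break-even share = 1 − 1/F: 3.5% at n=30 and 2.6% at n=40.
- SE change = √(F(1 − share)) − 1:

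| True site share | n=30 | n=40 |
|---|---|---|
| 0% | +1.8% | +1.3% |
| 10% | −3.5% | −3.9% |
| 20% | −9.0% | −9.4% |
| 30% | −14.9% | −15.2% |

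The 0% row is an average over allocations. At n=30 the 95th percentile of F is 1.050, a loss of about 2.5%, and the worst of the 28 pairwise contrasts loses about 3.9% on average. At n=40 these are about 1.8% and 2.9%.

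The 3.5% is a true share, not an observed R². Seven degrees of freedom explain about 7/202 = 3.5% by chance, so the matching observed partial R² at n=30 is about 6.8%.

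In simulated trials, the planned model's type I error under permutation was 0.038 to 0.056 (simulation error about 0.004).

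**Position-balanced sites.** Suppose 40 subjects form five complete 8×8 Latin squares. Site then cancels from every contrast, and the true SE is √(2/40) = 0.224. The planned model's SE is √(2(1 + r·40/39)/40). If 30 of the 40 are kept at random, put f = (1 − 30/40)·40/39 = 0.256. The true SE is √(2(1+f·r)/30), and the model SE is √(2(1 + r(30−f)/29)/30).

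| True site share | r | Overstated, exact balance n=40 | Type I error | Overstated, 30 of 40 kept | Type I error |
|---|---|---|---|---|---|
| 10% | 0.111 | 5.5% | 0.039 | 4.1% | 0.041 |
| 20% | 0.250 | 12.1% | 0.028 | 8.7% | 0.033 |
| 30% | 0.429 | 20.0% | 0.019 | 13.9% | 0.026 |

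These are formula values. A simulation of the 30-of-40 case gave slightly less: 3.7%, 8.2% and 13.3%. If site has no effect, adding it costs nothing in SE at exact balance apart from 7 df, and about 0.4 to 0.5% with 30 of 40 kept (F = 1.009).

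**A smaller term.** Arm plus elbow-to-wrist position uses 1 + 3 = 4 df. Under permutation F is 1.020 at n=30 and 1.015 at n=40, so break-even is 2.0% and 1.5%.

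**The case against.** The strongest reply is that the plan contains no error. Treatment, baseline and random subject are a valid analysis of treatments randomised within subject. A reader might infer from the missing term that bandage comparisons are biased, that false positives increase, or that the primary result is affected. The documents support none of these. Randomising treatments to sites keeps the contrasts unbiased; type I error is nominal under permutation and below nominal under balance. Time to healing is analysed by Kaplan-Meier medians and a subject-level bootstrap, not by this model. All of that stands.

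The second reply is that nothing shows site matters. Protocol 4.2.1 requires uniform forearm skin color, Protocol 7.2.4.3 says "A certified laser specialist will create 8 uniform wounds on the volar forearms of each subject", and wounds are at least 4 cm apart. These features limit site differences but do not rule out a gradient along the forearm. Baseline may also take up a standing difference. If a 20% share before adjustment (r = 0.25) carries over with slope b, the remainder is 0.25(1−b)². At b=0.5 that is 0.0625, a share of about 6%, and the n=30 gain is about 1.3%. At b=0.7 it is 0.0225, about 2.2%, and adding site loses about 0.7%. This applies mainly to TEWL, because the grades and scar score on intact skin are probably near their floor. The sign of the gain is therefore unknown in advance.

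Third, 1.8% is not a ceiling on the loss: single allocations and single contrasts can lose more, as shown above. The loss is still small.

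**Conclusion.** The omission is real, and its consequence is modest. The planned analysis of the four endpoints is valid; including site is a cheap, optional way to narrow intervals in an exploratory comparison. Under permutation at n=30 the trade is an average SE loss of 1.8% if site does nothing against a gain of about 9% at a 20% share, with break-even at a true share of about 3.5%. Under a balanced scheme the case is stronger: if sites differ, the planned SEs are overstated and the tests conservative, and the cost of the term is close to nil. If sites do not differ, the planned SEs are correct under either scheme.

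The conclusion rests on an assumed site share, complete data, an additive site effect and, for the 30-of-40 figures, random loss from five complete squares. A reader might take the table as evidence that precision will improve; it shows only what would follow if site mattered to that degree.

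**What to change.** For TEWL, erythema, edema and scar score, add test site (1 to 8) as a fixed class effect: `CLASS subjid treatment site; MODEL chg = treatment site baseline / solution ddfm=contain; RANDOM subjid;`. If a gradient or arm difference is the main worry, use arm plus elbow-to-wrist position (4 df) instead. Choose one before the data are analysed. Align SAP 4.5 and Protocol 8.3.2, and add a sentence to Protocol 6.6 or the SAP saying whether sites are permuted or position-balanced.

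No new data are needed. The cost is 7 (or 4) residual degrees of freedom, a small average loss in SE if site has no effect, and a wording change. Changing Protocol 8.3.2 is an amendment that needs Sponsor and IRB/IEC approval under Protocol 10.1.
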